281 First, sites were stratified based on risk group (MSM and PWID) and then additional
282 restriction criteria were used to ensure balance, first within strata and then overall. Within strata,
283 restrictions were made on the basis of geography, HIV prevalence and the primary outcome:
284 HCT in the prior 12 months (**Table 3**). Additional restrictions were made on outcomes among
285 HIV positive persons. All within-strata restrictions were based on RDS-weighted proportions of
286 the outcomes. After strata-specific restrictions were made, the two strata were combined to
287 derive a combined set of allocations. Final restrictions were made using the same outcomes with
288 the exception that both RDS-weighted and unweighted proportions were considered.

289 Restrictions related to geography and HIV prevalence were imposed because both were
290 related to the stage of the HIV epidemic in the target population and HIV service availability.
291 Further, geographic restrictions were important for political reasons, such that all intervention

292 sites were not restricted to one region or state. Additional covariates used in the restriction
293 process represented the primary and secondary outcomes. Of a total 232,848 possible
294 allocations, 596 allocations remained after all restrictions. Across all combinations, there were
295 only two sites that had >75% chance of being randomized to the same arm [53]. Three
296 individuals independent from the study who were blinded to the allocation sequence associated
297 with each of the possible numbers chosen (e.g., 001 to 596) were asked to draw numbered balls
298 from an opaque container to arrive at the final 3 digit number, corresponding to a numbered
299 randomization combination. A recording of the randomization is available at:

300 https://www.youtube.com/watch?v=vmHYHgv_uS0. The final allocation is shown in **Figure 2**.

301

302 *Intervention implementation.*

303 Venue selection. In each intervention site, venues were selected for scale-up following
304 discussions between the State AIDS Control Society, NGO leaders, MSM/PWID community
305 members and study investigators. In all cities, only one site was selected for scale up unless
306 mobility within the city was restricted due to distance or unsafe circumstances, in which case
307 more than one ICC was scaled-up (e.g., Imphal – 3 , Chandigarh – 2, Bilaspur – 2). For the

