391 control clusters of 10-40%, a range of 350-1000 persons in each cluster for HIV-negative
392 outcomes, an RDS design effect of 2, a two-sided α of 0.05, power=0.80 and a within-stratum
393 coefficient of variation ranging from 0.10 to 0.40. We incorporated the RDS design effect
394 (relative to simple random sampling) by doubling the sample size required per cluster after
395 calculating power. For the primary outcome, with 11 intervention and 11 control clusters, we
396 will have 80% power to detect an absolute difference of 12% in the prevalence of the primary
397 outcome in intervention and control clusters (e.g., 42% and 30%, respectively) with a within-
398 stratum coefficient of variation of 0.25 and 1000 participants in each cluster.

399 Our trial was powered to be able to detect differences in the primary outcome, but we
400 also calculated power for secondary outcomes. Power for secondary outcomes that include the
401 full sample (e.g., proportion of PWID reporting sharing injection equipment in the prior 6
402 months) was similar to that for primary outcomes as the methods and the range of outcome
403 prevalence in control clusters was within the range of what was considered for the primary
404 outcome. Power was relatively insensitive to the within-cluster sample size so our ability to
405 detect outcome differences for outcomes where only HIV positive subjects are considered is
406 similar to outcomes where the full RDS sample is used. For outcomes restricted to HIV-positive

407 subjects, we assumed a sample size of 100-300 persons per cluster. Power remained insensitive
408 to the cluster sample size down to a sample size of 100 per cluster. For example, with all other
409 assumptions held constant and an RDS sample size of 150, if the baseline prevalence of the
410 outcome is 30%, we will be able to detect a difference of 14 percentage points (e.g., 30% vs.
411 44%). For outcomes with lower baseline prevalence, we would be able to detect a smaller
412 difference (e.g., if 20% of HIV infected patients are engaged in care in the control sites, we
413 would have adequate power to detect a difference of 9 percentage points [20% vs. 29%]).

414

415 **Analysis plan**

416 *Community level.*

417 The primary analysis will be to compare the prevalence of community-level outcomes
418 across intervention and control clusters, adjusting for pre-intervention prevalence levels. For a

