419 given outcome, we will first log-transform the 22 cluster-level proportions obtained from the
420 post-intervention RDS. Then, via weighted least squares linear regression, these will be
421 regressed on a dummy term for the control arm (vs. intervention), another for the MSM stratum
422 (vs. PWID), and a term for the log-transformed cluster-level pre-intervention proportions. The
423 exponentiated coefficient for the control arm term is thus the prevalence risk ratio (PRR), and $(1-$
424 $PRR) \times 100\%$ is the percentage increase in service utilization associated with the intervention.
425 The primary analyses will be conducted using the RDS-II weighted cluster-level proportions
426 from both pre- and post-intervention RDS samples. These RDS-II weights, which account for
427 personal network size (number of PWID or MSM seen in the past 30 days) will be calculated
428 using the RDS Analyst Software Version 0.5 (<http://hpmrg.org>). For secondary outcomes that are
429 continuous (e.g., community viral load) we will use a similar regression approach.

430 We will conduct several sensitivity analyses for the primary and all secondary outcomes
431 First, we will repeat analyses using unweighted cluster-level proportions from both the pre-and
432 post intervention RDS surveys. Second, we will consider adjustment for demographic covariates
433 (age, sex, marital status and educational attainment) measured at the post-intervention RDS that
434 are associated with the outcome and are differentially distributed across intervention and control
435 clusters. We will consider adjustment for these factors if the p values for associations with the
436 outcome and the intervention vs. control clusters are <0.05 and the OR is >2 or <0.5 . A two-
437 stage approach will be used when adjusting for individual-level covariates: at the first stage, for a
438 prevalence outcome, individual responses are modeled with a logistic regression model adjusting
439 for all relevant covariates except the dummy term for control vs. intervention. In the second
440 stage, observed and expected prevalence counts for each cluster are calculated, followed by t-
441 test-like analyses of log-transformed ratios of observed to expected [53]. We will also consider
442 an approach that models the difference in outcome prevalence between the pre- and post-
443 intervention surveys using the same cluster-level comparison approach. We will also consider

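### Allocation was balanced on HIV prevalence and geography but the primary model adjusts for neither, so its standard error may be conservative and some power may go unclaimed

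*Combined protocol and SAP*

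**What the plan says.** The Randomization section describes stratified, restricted allocation that cut 232,848 possible allocations to 596. Within strata the restrictions used geography, HIV prevalence and HIV testing in the prior 12 months (the primary outcome), with further limits on outcomes among HIV-positive participants; Table 3 gives the rules. The text says "Restrictions related to geography and HIV prevalence were imposed because both were" connected with epidemic stage and the availability of HIV services. It adds a political reason for geography.

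Under Analysis plan, Community level, the log-transformed post-intervention proportions are "regressed on a dummy term for the control arm (vs. intervention), another for the MSM stratum", together with the log pre-intervention proportion. Two of the balancing factors, stratum and baseline testing, are therefore in the model. HIV prevalence and region are not, and no reason is given.

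The other analyses do not fill the gap by name. Covariate sensitivity analyses list demographics. The multilevel models permit cluster-level baseline covariates but name neither factor. Region appears only in within-stratum subgroup analyses. No analysis uses the set of 596 allowed allocations.

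**The concern.** Forcing balance on a factor that predicts the outcome removes that factor from the true sampling variance of the arm contrast. If the factor is left out of the model, its contribution stays in the residual variance. The reported standard error is then larger than the true one, the test rejects a true null less than 5% of the time, and the confidence interval is wider than it need be.

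The plan itself gives a reason to think these two factors are prognostic: it ties them to service availability, and the primary outcome is use of a service. With 22 clusters, a few points of power are worth having, and baseline HIV prevalence has already been measured in every city.

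**Working it through.** **1. The plan's own figure.** Inputs from Statistical power: 11 clusters per arm, 42% vs 30%, two-sided alpha 0.05, design effect 2 (so m = 1000/2 = 500), and "stratum coefficient of variation of 0.25 and 1000 participants in each cluster". The unmatched cluster formula is

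c = 1 + (1.96 + 0.84)² × [p0(1−p0)/m + p1(1−p1)/m + k²(p0² + p1²)] / (p1 − p0)².

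- Bracket: 0.21/500 + 0.2436/500 + 0.0625 × (0.09 + 0.1764) = 0.01756.
- c = 1 + 7.85 × 0.01756/0.0144 = 10.57, so 11 per arm.
- Power at c = 11: Φ(√(10 × 0.0144/0.01756) − 1.96) = Φ(0.90) = 81.7%.

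The stated 80% reproduces. It uses only a within-stratum coefficient of variation and takes no credit for any covariate.

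**2. Size of the mismatch in closed form.** The planned model has 22 − 4 = 18 residual df. Let R be the share of residual between-city variance explained by a perfectly balanced omitted factor. Then model SE / true SE ≈ 1/√(1−R), and the effective critical value is 2.101/√(1−R).

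- R = 0: ratio 1.00, type I error 5.0%.
- R = 0.10: ratio 1.054, critical value 2.215, type I error 4.0%.
- R = 0.25: ratio 1.155, critical value 2.426, type I error 2.6%.

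The documents do not give R; these values are assumptions.

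**3. Simulation under restricted allocation.** The two strata give C(10,5) × C(12,6) = 252 × 924 = 232,848 allocations, matching the protocol. The Table 3 geography rules leave 120 × 360 = 43,200. The 600 best balanced on baseline testing and HIV prevalence stood in for the 596. Assumptions: log SD 0.25, pre/post correlation 0.5, sampling variance at 30% with 500 effective participants, log ratio 0.27 for power, 6,000 trials per scenario.

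| Share explained by HIV prevalence (assumed) | Type I, planned | Type I, with term | Power, planned | Power, with term |
|---|---|---|---|---|
| 0% | 4.6% | 4.6% | 74.8% | 74.3% |
| 10% | 4.4% | 5.0% | 75.2% | 78.1% |
| 25% | 3.0% | 4.8% | 75.8% | 83.3% |

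A repeat run gave power changes of −0.3 (74.1% to 73.8%), +3.1 (75.7% to 78.8%) and +8.2 points (77.1% to 85.3%). At a 5% share the gain was about 1 point (73% to 74%), within Monte Carlo error of about 0.9.

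**4. A second set-up.** This one limited arm differences to under 0.35 SD within stratum on both variables, with a log ratio of 0.85 × 0.336 and 3,000 runs. Adding HIV prevalence alone moved power from 81.7% to 81.3% with nothing explained, and from 84.0% to 85.9% at a 10% share, where the planned model's type I error was 3.6%. The largest loss was 1 point (84.2% to 83.2%), when region explained 10% and HIV prevalence nothing.

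**5. Why region is different.** Six region groups in place of the stratum dummy cost 4 more df. Adding both region and HIV prevalence in the second set-up lowered power from 81.7% to 76.2% with nothing explained, and from 84.2% to 81.1% when region alone explained 10%. Break-even on expected interval half-width is about 0.7% of residual variance for HIV prevalence alone (17 df) and about 4.4% for both (13 df).

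**The case against.** The strongest objection is that the protocol's link to service availability is marginal. What matters is whether HIV prevalence or region predicts later testing *after* stratum and the same city's baseline testing level. Baseline testing is the most direct measure of testing access, and it is both a balancing factor and a model term. It may absorb most of the signal. This stands: the effect is conditional, and at small shares it is negligible.

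A reader might infer that the standard error *is* too large and power *is* lost. The documents report nothing that would establish that. A reader might also infer that the omission squanders power the restriction was meant to secure. The Randomization section states its purpose as avoiding large imbalances between arms, with a political reason for geography; it does not mention power, and the balance holds whatever the model contains.

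It is also fair that the multilevel sensitivity models could accommodate HIV prevalence. They do not name it and are only to be considered, so this softens the point without answering it. Finally, any added term needs a stated scale, estimator and scope: Table 3 used RDS-I for prevalence within strata, whereas the primary analysis uses RDS-II.

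**Conclusion.** The point holds in conditional form. Two factors used to restrict allocation are missing from the primary model. If either retains prognostic value given stratum and baseline testing, the planned test is conservative. For HIV prevalence the assumed range runs from no effect at 0%, through about 3 points of unclaimed power at 10% (2 in the second set-up), to about 8 points at 25%.

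The stronger reading, that the trial is underpowered or its inference invalid, is not supported. The 80% figure reproduces without covariate credit, the estimate is unbiased, and type I error is not inflated.

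The case for a change is the lopsided trade: 0.3 to 1 point lost at worst against several points gained at moderate shares. The figures assume normal log proportions, unweighted least squares (the plan specifies weighted, without stating the weights), HIV prevalence unrelated to baseline testing, and a stand-in for the actual 596 allocations.

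**What to change.** Before post-intervention outcomes are seen:

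- Add one term to the regression for the primary outcome: each city's pre-intervention HIV prevalence, RDS-II weighted and log-transformed to match the other terms. Test the arm coefficient on t with 22 − 5 = 17 df. Limit the change to the primary outcome; its value for the secondary outcomes has not been examined.
- Pre-specify, as a sensitivity check, a permutation p-value for the arm term over the 596 allowed allocations. This reflects the geographic restrictions without spending degrees of freedom. It held about 4–5% type I error in simulation. It is less powerful than the t-test when the balanced factors explain little, so the model-based result should stay primary.
- Do not add region dummies.

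The cost is a few lines of plan wording, a short program and one residual degree of freedom: about 0.3 to 1 point of power if HIV prevalence turns out not to be prognostic. No new data are needed.

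### With the arm dummy coded for control, (1 − PRR) × 100% is not the percentage increase over control: it gives 28.6% where the plan's own design values imply 40.0%

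*Combined protocol and SAP*

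**What the plan says.** The rule is in the combined protocol and SAP, Analysis plan, Community level. It has four steps.

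- The outcome is put on the log scale: "given outcome, we will first log-transform the 22 cluster-level proportions obtained from the" post-intervention survey.
- By weighted least squares, these values are "regressed on a dummy term for the control arm (vs. intervention), another for the MSM stratum", plus the log of the pre-intervention proportion. Control is therefore coded 1 and intervention is the reference.
- The "exponentiated coefficient for the control arm term is thus the prevalence risk ratio (PRR").
- The quantity (1 − PRR) × 100% "is the percentage increase in service utilization associated with the intervention".

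No other section defines the PRR or the percentage differently. The Statistical power section supplies the design values used below. For the primary outcome it gives "e.g., 42% and 30%, respectively", with intervention named first. For outcomes restricted to HIV-positive participants it gives 30% against 44%, and 20% in control sites against 29%.

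**The concern.** The control dummy is a legitimate choice. The fault is in the conversion that follows it. The formula 1 − ratio gives a percentage relative to the denominator of the ratio, and here the denominator is the intervention arm. A reader told that the intervention raised uptake by some percentage will take the level without the intervention as the base.

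This sentence is the plan's only rule for turning the fitted ratio into a percentage effect, and its paragraph covers the primary outcome, HIV counseling and testing in the prior 12 months. Under Dissemination, stakeholders are to decide whether to adopt the care-center model in the light of demonstrated effectiveness and cost. The error would be hard to notice because the wrong figure has the right sign and a plausible size.

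**Working it through.** **Inputs.** Control coded 1, intervention as reference, log-transformed proportions (Analysis plan, Community level). Planning prevalences 42% v 30%, 44% v 30% and 29% v 20%; 11 clusters per arm; within-stratum coefficient of variation (CV) 0.25; 1000 participants per cluster; RDS design effect 2; two-sided alpha 0.05 (Statistical power).

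**The plan's own figure.** The plan gives no numerical value for (1 − PRR) × 100%, so the check is on the design values. I took 1000/2 = 500 effective participants per cluster and the standard unmatched cluster-trial formula:

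c = 1 + (1.96 + 0.842)² × [0.30×0.70/500 + 0.42×0.58/500 + 0.25²×(0.30² + 0.42²)] / 0.12² = 10.57

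This rounds up to 11 per arm, and power with 11 per arm is 81.7%. The stated 80% is reproduced, so 42% v 30% is a fair basis for the example.

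**Algebra.** Let pI and pC be the adjusted prevalences in the intervention and control arms.

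- PRR = pC/pI
- As written: 1 − PRR = (pI − pC)/pI
- Increase over control: (pI − pC)/pC = 1/PRR − 1
- Ratio of the two: (1 − PRR)/(1/PRR − 1) = PRR
- Gap: (1/PRR − 1) − (1 − PRR) = (1 − PRR)²/PRR, which is never negative

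**Numbers.**

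| Intervention v control | PRR | As written, 1 − PRR | Over control, 1/PRR − 1 |
|---|---|---|---|
| 42% v 30% | 0.30/0.42 = 0.714 | 28.6% | 40.0% |
| 44% v 30% | 0.30/0.44 = 0.682 | 31.8% | 46.7% |
| 29% v 20% | 0.20/0.29 = 0.690 | 31.0% | 45.0% |
| 33% v 30% | 0.30/0.33 = 0.909 | 9.1% | 10.0% |
| 60% v 30% | 0.30/0.60 = 0.500 | 50.0% | 100.0% |

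The first three rows are the plan's values; the last two are illustrations. As a consistency check, 30% raised by 28.6% is 38.6%, not 42%; 30% raised by 40.0% is 42%.

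**Does reversing the coding rescue the sentence?** No. With intervention coded 1, the ratio at 42% v 30% is 1.40 and 1 − PRR is −40%, which reads as a decrease. Neither coding makes the formula correct.

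**Illustrative interval at 42% v 30%.** The documents give no standard error for the log PRR. I assume equal weights, no precision gain from the baseline covariate, and 22 − 4 = 18 degrees of freedom:

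SE = sqrt{[2×0.25² + 0.70/(0.30×500) + 0.58/(0.42×500)]/11} = 0.110

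This gives a PRR of 0.714 (95% CI 0.567 to 0.899). Converting the limits over the plan's CV range of 0.10 to 0.40:

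| CV | As written | Over control |
|---|---|---|
| 0.10 | 20.7% to 35.7% | 26.1% to 55.5% |
| 0.25 | 10.1% to 43.3% | 11.2% to 76.3% |
| 0.40 | −2.6% to 50.3% | −2.6% to 101.2% |

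**Model check.** I fitted the plan's regression (arm, stratum, log baseline proportion; equal weights) to constructed data with 30% in every control cluster and 42% in every intervention cluster. It returned exp(control coefficient) = 0.714, hence 28.6% as written and 40.0% over control. On one simulated set of 22 clusters, both arm codings gave |t| = 3.02 and p = 0.0073, with reciprocal ratios 0.727 and 1.376. Recoding does not alter the test.

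**The case against.** The strongest reply concerns weight rather than correctness. The PRR is the fitted effect measure, power is stated for absolute differences, and no success criterion uses the derived percentage. Anyone given the PRR and its direction can recover the right figure. All of that stands, and it limits the point to reporting. It does not excuse a prespecified effect percentage that is wrong.

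Four narrower objections also deserve an answer.

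- *Interval.* The plan never says that a confidence interval will be given for the percentage. True. The interval figures apply only if the limits are converted by the same formula, and they are illustrative. Understated is also meant in signed terms: for a limit on the wrong side of the null the written value is lower but larger in size (PRR 1.20 gives −20.0% against −16.7%).
- *Labelling.* The quantity 1 − PRR is coherent as the arm difference relative to intervention-arm prevalence, and the sentence names no base. Relabelling it would remove the error. But the sentence calls it an increase associated with the intervention, and the ordinary base for that is control.
- *Primary outcome.* The sentence speaks of service utilization, which the study aims mention separately from HIV testing. This carries little weight: the paragraph is written for any given outcome and offers no other conversion.
- *Examples.* The 44% v 30% example names no outcome, so it may not concern utilization. It shows the size of the gap at a design value and nothing more.

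**Conclusion.** The sentence is wrong as written. Under the stated coding, the formula expresses the effect relative to the intervention arm and so understates every increase by a factor equal to the PRR. At the primary planning values the shortfall is 11.4 percentage points (40.0% − 28.6%). It grows with the effect: a doubling would be reported as 50%, and no increase could reach 100%.

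The point figures follow from the plan's definitions and design values, with one interpretive step: that a percentage increase is taken over control. Only the interval figures need the further assumptions listed above.

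The error is confined to the derived percentage and any limits converted with it. I make no claim about outcomes meant to fall, since the sentence does not address them. It should be fixed, but it does not threaten the trial's inference.

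**What to change.** Replace the sentence in Analysis plan, Community level with one of these:

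1. Keep the control dummy, state that PRR = control/intervention, and report (1/PRR − 1) × 100% as the percentage increase relative to control.
2. Code intervention as 1, state that PRR = intervention/control, and report (PRR − 1) × 100%.

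The second puts the ratio and the percentage in the same direction and is easier to read. In either case, if an interval is given for the percentage, convert the PRR limits by the same formula; under option 1 the limits change places. State the numerator arm and the base explicitly.

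The cost is one sentence of wording, with no change to data, model, test or power. The document is dated 14 November 2016 and the post-intervention survey was expected to finish by April 2017, so on the plan's own timetable the correction could precede the analysis. If a percentage has already been produced by the written rule, it can be recomputed exactly from the PRR and its limits.

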108 awareness of HIV status, reduce injection-related and same-sex risk behavior, improve health,

109 reduce mortality, and decrease the infectiousness of HIV-infected persons in the community
110 through effective viral suppression. We will evaluate the community-level effectiveness of
111 MSM//PWID-focused integrated care centers (ICCs), which will provide core and group-specific
112 HIV prevention and treatment services at a single venue utilizing a cluster-randomized trial
113 design in 22 sites across India.

114

115 Our hypotheses are:

116 1) Establishing ICCs will increase access to HCT and knowledge of HIV status among MSM and
117 PWID.

118 2) In the subset of HIV-infected MSM and PWID, ICCs will increase access to care, use of ART
119 and will decrease community viral load.

120 3) Establishing ICCs will decrease transmission risk behaviors and HIV incidence among MSM
121 and PWID via improved access to prevention services (NSEP, OAT, IEC).

122

123 **METHODS/ DESIGN**

124 **Study design**

125 The study design is a cluster-randomized trial with parallel MSM and PWID strata. ICCs
126 were scaled-up and implemented at sites allocated to the intervention arm, and outcomes will be
127 assessed by pre- and post-intervention surveys at intervention and control sites (**Figure 1**). As
128 MSM and PWID are hidden populations with no sampling frame, respondent-driven sampling
129 (RDS) will be used to accrue samples for the two independent cross-sectional surveys. Sites (10
130 MSM and 12 PWID sites) were randomized in a 1:1 allocation ratio. The trial is currently
131 underway. The pre-intervention survey took place between September 2012 and December 2013;

132 the ICCs were scaled up between June 2014 and February 2015. Post-intervention survey
133 commenced in August 2016 and is expected to be complete by April 2017.

134 **Study sites**

135 Twenty-seven candidate sites were selected (15 PWID, 12 MSM; **Figure 2**) of which 22
136 were included in the trial. Sites were selected to represent regions of India where there was
137 preliminary evidence of high HIV prevalence or high risk of HIV acquisition through discussions
138 with the Targeted Interventions (TI) Division of NACO, India. We ensured sufficient distance
139 between sites to minimize potential overlap (contamination) between intervention and control
140 sites. MSM sites were selected to represent cities with established HIV epidemics among MSM,

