444 individual-level analyses using multi-level random effects regression approaches (Stata
445 GLLAMMs program) to account for dependence of responses within clusters [54-56]. These
446 models allow inclusion of fixed effects (e.g., intervention), random effects (e.g., clusters),
447 adjustment for pre-intervention covariates at the individual and cluster level, and incorporation
448 of scaled RDS weights as sampling weights. Finally, we will conduct descriptive analyses of the
449 HIV care continuum, before and after the intervention phase of the study, in which completion of
450 earlier steps are assumed to be necessary to complete later steps. Additionally, we will consider
451 sensitivity analyses of outcomes in the HIV care continuum, where biologic markers such as

452 HIV RNA and serum antiretroviral drug testing, are used to supplement self-reported data on
453 access to care.

454 Several subgroup analyses are also planned. First, we will analyze all outcomes
455 separately within each stratum (PWID and MSM). Using the combined sample of MSM and
456 PWID sites, we will further compare all outcomes within subgroups defined by age, marital
457 status, educational attainment, substance use (drug and alcohol use), and personal network size
458 (number of persons in risk group [PWID or MSM] known and seen in the prior 30 days). Using
459 only the PWID sites, we will also analyze subgroup differences by age, sex, marital status,
460 educational attainment, substance use (including alcohol use), personal network size and region.
461 In the MSM sites, we will also analyze subgroup differences by age, sexual identity, marital
462 status, educational attainment, substance use (including alcohol use), personal network size and
463 region. We also plan subgroup analyses by HIV serostatus and awareness of status for risk
464 behaviors, HIV testing of spouses, substance use, stigma, and depression.

465

466 *Network- and individual-levels.*

467 Network effects will be ascertained by comparing utilization of ICCs and services within
468 ICCs across networks as defined by RDS. For example, we will examine utilization patterns
469 across recruiters and recruits in the evaluation RDS. We will also ascertain whether utilization of
470 ICCs varied by wave of RDS. Individual-level comparisons will draw on data from post-
471 intervention RDS participants in the intervention clusters, in which extra questions will address

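### The optional individual-level random-effects models carry no small-sample correction, although arm varies over only 22 cities; uncorrected normal-based tests would run at roughly 7-9% instead of 5%

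*Combined protocol and SAP*

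**What the plan says.** The primary analysis (Analysis plan, Community level) is a weighted least squares regression of 22 log-transformed city proportions on arm, stratum and the log baseline proportion. Sensitivity analyses for the primary and all secondary outcomes follow. The last modelling option is "individual-level analyses using multi-level random effects regression approaches (Stata" with the program named on the next line: "GLLAMMs program) to account for dependence of responses within clusters [54-56]. These" models may hold fixed and random effects, adjust for pre-intervention covariates at person and city level, and allow incorporation "of scaled RDS weights as sampling weights".

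Reference 56, cited for this approach, is by its title a maximum-likelihood method. The section does not say which covariates enter, which variance estimator is used, or against which distribution the arm term is tested. Elsewhere the plan does respect the number of cities: the primary model works on city-level values, and the covariate-adjusted two-stage analysis ends in a comparison of t-test type.

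On the design, the sites ("MSM and 12 PWID sites) were randomized in a 1:1 allocation ratio") were allocated by a draw from 596 permitted allocations out of 232,848 (Randomization; Table 3).

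**The concern.** Arm is a property of the city. About 1,000 respondents per city fix each city's own proportion well, but they add almost no information about how much cities differ from one another, and that variation drives the uncertainty of the arm effect. With arm, stratum and baseline fitted, 22 - 4 = 18 degrees of freedom remain. A maximum-likelihood variance divides in effect by 22 where 18 is needed, and a normal critical value of 1.96 replaces the t value of 2.101. Both errors make the interval too narrow.

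These models serve as a check on the primary result and may be applied to all 26 outcomes in Table 1. A check that rejects too often can seem to confirm a primary result, or to find an effect where the cluster-level test finds none. The plan also analyses every outcome within strata of 12 and 10 cities, where the same models, if used, would be further off.

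**Working it through.** **Inputs from the Statistical power section.** "outcomes, an RDS design effect of 2, a two-sided α of 0.05, power=0.80 and a within-stratum" coefficient of variation k; "with 11 intervention and 11 control clusters, we" have 80% power for the primary "outcome in intervention and control clusters (e.g., 42% and 30%, respectively) with a within"-"stratum coefficient of variation of 0.25 and 1000 participants in each cluster".

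**Step 1: the plan's own figure.** With m = 1000/2 = 500 effective persons per city,

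c = 1 + (1.960 + 0.842)² × [p0(1-p0)/m + p1(1-p1)/m + k²(p0² + p1²)] / (p0 - p1)²

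The bracket is 0.21/500 + 0.2436/500 + 0.0625 × (0.09 + 0.1764) = 0.00042 + 0.00049 + 0.01665 = 0.01756. Then c = 1 + 7.849 × 0.01756/0.0144 = 10.57, so 11 cities per arm. Power at 11 is 81.7%, which agrees with the stated 80%. The between-city part is 0.01665/0.01756 = 95% of the variance, so the number of cities governs inference on arm. The plan states no type I error for the individual-level models.

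**Step 2: size of an uncorrected test, by formula.** With G = 22 cities and p city-level parameters including the intercept, a maximum-likelihood Wald test with a normal reference rejects when |t| on G - p df exceeds 1.96 × √((G - p)/G).

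| City-level terms | df | Threshold | ML variance, normal | Unbiased variance, normal |
|---|---|---|---|---|
| arm | 20 | 1.869 | 7.6% | 6.4% |
| arm, stratum | 19 | 1.821 | 8.4% | 6.5% |
| arm, stratum, baseline | 18 | 1.773 | 9.3% | 6.6% |

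At 18 df, a valid interval is wider than the uncorrected one by a factor of (2.101/1.960) × √(22/18) = 1.185.

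**Step 3: simulation without the allocation restrictions.** In 40,000 city-level fits, a sandwich variance with a normal reference gave 7.5%, 8.5% and 9.4% for the three rows (6.9%, 7.8% and 8.8% with the 22/21 factor). A direct individual-level simulation used 2,500 runs of a random-intercept logistic model with 22 cities of 1,000, prevalence 30%, k = 0.25 and lognormal weights with design effect about 2. The Monte Carlo standard error is about 0.55 points. The sandwich test with a normal reference gave:

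- arm, stratum and baseline: 8.3% weighted, 8.6% unweighted;
- arm only: 8.4% weighted, 8.5% unweighted.

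The weights make no visible difference.

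**Step 4: simulation with restricted randomisation.** Balancing baseline by design reduces the true variance of the arm contrast. A model that omits baseline does not see that gain, so its standard error is too large, which offsets the small-sample bias. Two sets of city-level simulations, with different assumed tolerances and correlations, gave for the maximum-likelihood test with a normal reference:

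- arm and stratum only: about 5% in one set, 1.1% to 7.5% in the other;
- arm, stratum and baseline: about 8-10% in one set, 5.3% to 9.5% in the other. The lower values, 5.3% to 7.6%, arose when five covariates were balanced.

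**Step 5: the corrections.** A residual-df variance with t on 18 df gave 5.0% without restriction. Under restriction, t on 18 df and permutation over the allowed allocations gave about 4-5%. Changing only the reference to t on 18 df and keeping the sandwich variance left 6.8-6.9% with arm, stratum and baseline, so the variance needs correcting too.

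**Step 6: within strata.** With arm and baseline, the Step 2 formula gives 12.4% for 12 cities (9 df) and 14.5% for 10 cities (7 df), if these models are used there.

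**The case against.** The strongest reply is that the plan never specifies a normal-based test. It says only that these models will be considered, and an analyst could apply a correction unprompted. That stands: the normal reference is an inference from the named software, the cited maximum-likelihood method and the absence of any correction. But following the text as written leads to the uncorrected test, and nothing in it asks for anything else.

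A second reply is that the simple formula ignores the restricted randomisation. This also stands in part. Table 3 balances the baseline primary outcome, HIV prevalence, four outcomes among HIV-positive persons and geography. In a model without baseline, the excess can disappear or reverse. With baseline included, most of it returns.

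A third reply is that the analysis is optional and nothing lets it override the primary test. That is correct and limits the importance of the point.

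A reader might also infer that using RDS weights as sampling weights produces the inflation. The weighted and unweighted simulations do not support that.

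**Conclusion.** The point holds as a missing small-sample provision in an optional sensitivity analysis. Uncorrected, and with arm, stratum and baseline in the model, the nominal 5% test would have a type I error of roughly 7-9%. This rests on assumptions outside the documents: a normal reference, the primary model's terms carried over, normally distributed city effects, and assumed baseline correlations and balance tolerances. Looser balance moves the size towards 8-9%; tight balance on several covariates moves it towards 5%.

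It would be tempting to say that the trial's type I error is 9%, or that its main conclusion is at risk. The documents support neither. A value near 9% is towards the upper end of a range that depends on the design. The primary analysis is a linear regression on 22 city values, for which residual degrees of freedom are available in the ordinary way. The importance is low, but the remedy is a better method at almost no cost.

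**What to change.** Add to the Community level section, for the individual-level models:

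- Include stratum and the baseline city proportion as fixed terms.
- Obtain the arm p-value by refitting over the 596 allowed allocations. This respects the restriction and gives a resolution of 1/596 = 0.0017. Alternatively, use a small-sample-corrected variance with a t reference on 18 df (22 cities minus intercept, arm, stratum and baseline). Changing the reference alone is not enough.
- In within-stratum analyses, and for outcomes defined in one stratum only, reduce the df: with intercept, arm and baseline, 10 - 3 = 7 for MSM and 12 - 3 = 9 for PWID. Subtract one more for each further city-level covariate. If permutation is used there, first count the distinct patterns that the 596 allocations leave in that stratum, since the documents do not give that number.

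The cost is a sentence or two of text, some extra computing for the refits, and slightly wider intervals in a sensitivity analysis. The primary analysis and the sample size do not change.
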